2.1 Section 1, Summary

Correction of error:

In need of treatment intensification is defined as an HbA_{1c} level of 7-10% (53-856 mmol/mol), both inclusive.

2.2 Section 2, Flow chart

Specification of visit window at P42 : ~~±3~~ +3

Addition of 'x' for hypoglycaemic episodes at P42, table 2-1, to highlight that hypoglycaemic episodes are collected in the follow up period : x

Addition of 'x' for hypoglycaemic episodes at P42, table 2-2, to highlight that hypoglycaemic episodes are collected in the follow up period: x

Clarification of text in foot note n:

Two follow-up visits are to be conducted. The first (V41) must take place no earlier than seven days and no later than 12 days after the EOT visit (V40). The last follow-up visit (P42) will take place ~~approximately no earlier than~~ 30 days after the EOT visit (V40) and ~~no later than~~ 33 days after the EOT visit (V40) and will be conducted as a phone contact (P42).

Clarification of foot note o:

At the abbreviated visits (V28a and V40a) HbA_{1c} samples and information on adverse events (AEs) *including hypoglycaemic episodes* will be collected

Addition of new foot note 'p' for 9-point-profile at V40 : ^P

Addition of new foot note p, to clarify that 9-point-profile is not required at V40 for subjects prematurely discontinued :

^p *For subjects prematurely discontinued from trial insulin products the 9-point-profile is omitted at visit corresponding to V40*

2.3 Section 4.2.2.1, Supportive secondary efficacy endpoints

Update of supportive secondary efficacy endpoints to implement new guidelines from FDA:

- At 26 weeks:
 - Responder (Yes/No) for HbA_{1c} after 26 weeks:
 - HbA_{1c} <7%
 - HbA_{1c} <7% without nocturnal (00:01-05:59) *severe or* blood glucose (BG) confirmed symptomatic hypoglycaemia
 - *HbA_{1c} < 7% without severe or BG confirmed symptomatic hypoglycaemia*
- At 38 weeks:
 - Responder (Yes/No) for HbA1c after 38 weeks:
 - HbA_{1c} <7%
 - HbA_{1c} <7% without nocturnal (00:01-05:59) *severe or* blood glucose (BG) confirmed symptomatic hypoglycaemia
 - *HbA_{1c} < 7% without severe or BG confirmed symptomatic hypoglycaemia*

2.4 Section 5.2, Rationale for trial design

Clarification of the rationale for trial design to highlight that hypoglycaemic episodes are to be collected in the follow up period:

A 30-day follow-up (P42) after last trial insulin treatment (V40) will be performed in order to collect information about antidiabetic treatment and adverse events (AEs) *including hypoglycaemic episodes* occurring between V41 and P42.

2.5 Section 6.5, Rescue criteria

Correction of rescue criteria text to clarify which SMPG values are to be used:

If any of the fasting SMPG values taken on three consecutive days or if any of the FPG samples analysed by the central laboratory exceed the limit of:

- 15.0 mmol/L (270 mg/dL) from baseline to end of week 12
- 13.3 mmol/L (240 mg/dL) from week 13 to end of week 38

and if no treatable inter current cause for the hyperglycaemia has been identified, the subject must be called for a confirmatory FPG measurement at a scheduled or unscheduled visit as soon as possible.

2.6 Section 7, Milestones

Change of timelines to reflect that recruitment period has been extended:

Planned duration of recruitment period (i.e. first patient first visit (FPFV) – last patient first visit (LPFV)): *169 weeks and 3 days*

Planned date for FPFV: 20 Sep 2016

Planned date for last patient last visit (LPLV): *16 Nov 12 Dec 2017*

2.7 Section 8.1.5, Diaries

Correction to specify when diaries are provided to subjects:

At each clinic visit, the subjects must receive diaries related to the following visit and/or phone contact(s). The diaries dispensed to subjects should be collected at the following clinic visit.

However, for ~~the screening visit (V1)~~, the 30-days follow-up visit (P42) and the monthly phone contacts (in case of pre-term discontinuation of trial insulin products) no diaries will be provided.

2.8 Section 8.1.9, Follow-up visits

Clarification to highlight that hypoglycaemic episodes are to be collected at last follow up visit (P42) and at potential monthly phone contacts (Px):

For the last follow-up visit (P42) and potential monthly phone contacts (Px), no paper diary will be provided. Consequently, source data for these phone contacts will be the notes written in the subject's medical record. At these contacts only information about antidiabetic treatment and AEs *including hypoglycaemic episodes* will be collected.

2.9 Section 8.1.11, Premature discontinuation of trial product

Clarification to highlight that 9-point-profile is not needed at the visit corresponding to V40 for subjects prematurely discontinued from trial product:

In case of premature discontinuation of trial product the investigator should make all effort to call the subject in for an unscheduled visit as soon as possible and must aim to undertake procedures similar to those for the EOT visit (V40), *except 9-point-profile but* including fasting blood sampling and hand-out of 'washout' insulin products (refer to Section 5.3.3) to be used in the period between the EOT visit (V40) and the 7-day follow-up visit (V41), where the last AB sampling will be performed.

2.10 Section 8.2.5, Concomitant medication

To clarify the definition and the reporting requirements for concomitant medications:

A concomitant medication is any medication, other than the trial product(s), which is taken during the trial, including the screening and follow-up periods.

Details of any concomitant medication must be recorded at the screening visit (V1), including OAD treatment and pre-trial basal insulin, which subjects continue using between the screening visit (V1) and the randomisation visit (V2). For details on OAD treatment, refer to Section 5.4.

The information collected for each anti-diabetic concomitant medication includes trade name or generic name, indication, total daily dose and route of administration, start date and stop date or continuation. For concomitant medication other than anti-diabetic concomitant medication only trade name or generic name, indication, start date and stop date or continuation are to be collected.

In case the concomitant medication is a systemic treatment which in the investigator's opinion could interfere with the glucose metabolism (e.g. treatment with orlistat, thyroid hormones, or corticosteroids – refer to exclusion criterion 14 (Section 6.3)), this information needs to be captured in the eCRF.

Changes in concomitant medication must be recorded at each visit as they occur.

~~The information collected for each concomitant medication includes trade name or generic name, indication, total daily dose and route of administration, start date and stop date or continuation.~~

If a change is due to an AE, then this must be reported according to Section 12.

~~In case the concomitant medication is a systemic treatment which in the investigator's opinion could interfere with the glucose metabolism (e.g. treatment with orlistat, thyroid hormones, or corticosteroids – refer to exclusion criterion 14 (Section 6.3)), this information needs to be captured in the eCRF.~~

If the change influences the subject's eligibility to continue in the trial or trial product treatment (refer to premature discontinuation criterion 4, section 6.6), the monitor must be informed.

2.11 Section 8.4.8, Hypoglycaemic episodes

Specification of process for recording of hypoglycaemic episodes during follow-up period:

All plasma glucose values:

- ≤ 3.9 mmol/L (70 mg/dL) or
- > 3.9 mmol/L (70 mg/dL) occurring in conjunction with hypoglycaemic symptoms

should be reported in the diary according to the instructions below throughout the trial from

randomisation (Visit 2) to the follow-up (Visit 41). *Hypoglycaemic episodes occurring between Visit 41 and the last follow up visit (P42) should be recorded on a hypoglycaemic episode form in the eCRF.*

2.12 Section 8.5.3.1, Haematology and Biochemistry assessments

Clarification that lab parameters will be analysed at screening and not at randomisation as previously indicated:

The below haematology and biochemistry parameters will be analysed at the ~~randomisation screening visit (V2V1)~~, prior to the intensification period (V28) and at the end-of-trial visit (V40), please refer to the flow chart (Section 2).

2.13 Section 12.1.1, Adverse event

Correction of cross-reference to a wrong section in the protocol:

Non-serious hypoglycaemia is an AE, but is reported on a hypoglycaemic episode form instead of an AE form, see Section ~~8.4.7. 8.4.8~~

2.14 Section 14, Monitoring procedures

Deletion of US requirement as this is wrong:

A follow-up letter (paper or electronic) will be sent to the investigator following each monitoring visit. This should address any action to be taken. ~~For U.S.: the follow up letter must be signed by the investigator.~~

2.15 Section 17.5.1, Efficacy endpoints

Update of supportive secondary efficacy endpoints to implement new guidelines from FDA:

Responder for HbA_{1c}

- **Responder (Yes/No) for HbA_{1c} after 26 weeks:**
 - HbA_{1c} <7%
 - HbA_{1c} <7% without nocturnal (00:01-05:59) ~~(BG)~~ severe or BG confirmed symptomatic hypoglycaemia
 - HbA_{1c} < 7% without severe or BG confirmed symptomatic hypoglycaemia
- **Responder (Yes/No) for HbA1c after 38 weeks:**
 - HbA_{1c} <7%
 - HbA_{1c} <7% without nocturnal (00:01-05:59) ~~(BG)~~ severe or BG confirmed symptomatic hypoglycaemia

- *HbA_{1c} < 7% without severe or BG confirmed symptomatic hypoglycaemia*

Subjects with less than 16 weeks of treatment will be set as non-responders. ~~Nocturnal Hypoglycaemic episodes will be based on the available data.~~

2.16 Section 17.5.2, Safety endpoints

Update of supportive secondary efficacy endpoints to implement new guidelines from FDA:

For endpoints addressing the hypoglycaemic rate in the 26 weeks or the 38 weeks period, a negative binomial model will be used, including treatment, previous insulin treatment regimen, previous OAD treatment, sex, and region as factors and age as covariate. The model will use a log-link function and the logarithm of the time period in which a hypoglycaemic episode was considered treatment emergent as offset. *The treatment rate ratios will be estimated and 95% confidence intervals will be calculated.*

~~The rationale for investigating the hypoglycaemic rate during the maintenance is to reflect long term use, as prior to this period (the titration period) the glycaemic control might be unstable. For endpoints addressing hypoglycaemic rate in the maintenance period, a negative binomial regression model using data from both the titration and maintenance periods will be used. This is done to comply with the randomisation principle, i.e. to include all randomised subjects in the analyses, also those who withdrew during the titration period. The model will use a log-link function and the logarithm of the time period in which a hypoglycaemic episode was considered treatment emergent as offset. Subject will be included as a random effect. The model includes treatment, previous insulin treatment regimen, previous OAD treatment, sex, region and period (titration or maintenance) as factors and age as covariate. The interaction between each factor and covariate with period will also be included.~~

~~From the above negative binomial models the treatment rate ratios will be estimated and 95% confidence intervals will be calculated.~~

The rationale for investigating the hypoglycaemic rate during the maintenance is to reflect long term use, as prior to this period (the titration period) the glycaemic control might be unstable. For endpoints addressing hypoglycaemic rate in the maintenance period, subjects that discontinue randomised treatment during the maintenance period will contribute with the available data from the maintenance period. For subjects that discontinue randomised treatment during the 16 week titration period, the number of events in the maintenance period will be imputed based on data from the maintenance period for subjects that discontinued randomised treatment during the maintenance period. For these subjects, the number of events will be imputed corresponding to a 10 weeks maintenance period as follows:

- *In the first step, 1000 samples from the posterior distribution of model parameters are extracted. The model is fitted to the on-treatment maintenance data for subjects that discontinued randomised treatment during the maintenance period for each treatment arm separately. This is done using a Bayes negative binomial log-link model with the same factors, covariates and offset as in the analyses of hypoglycaemic episodes described above. The 1000 samples are used as sampled parameter estimates in the next step.*
- *For each sample of model parameters, the total number of hypoglycaemic events in the maintenance period for subjects that discontinued randomised treatment in the titration period is imputed as a random number of events from a negative binomial distribution using the sampled parameters.*
- *For each of the 1000 imputed data sets, that now have maintenance period data for all randomised subjects, the mean treatment ratio is estimated using the same negative binomial model as in the analyses of hypoglycaemic episodes described above.*
- *The estimates and standard deviations for the 1000 imputed data sets are pooled to one estimate and associated standard deviation using Rubin's formula. From these the 95% confidence interval for the treatment ratio and the associated p-value are calculated.*

If the above model cannot fit due to sparse data, the model in step 1 is fitted to the on-treatment data for subjects that discontinued randomised treatment during either titration or maintenance, i.e. do not complete the scheduled 26 weeks of treatment. If this model cannot fit either, factors will be left out one by-one in the model using data from all subjects discontinuing randomised treatment before week 26 in the following order, until a model fits:

- *sex*
- *age*
- *region*
- *previous insulin treatment regimen*
- *previous OAD treatment*

2.17 Appendix A, section 3.6.2

Clarification of titration procedure:

If HbA_{1c} at week 32 is $\geq 7.0\%$ IAsp treatment should be further intensified with an additional dose of IAsp initiated at 4U, if deemed necessary by the investigator.

Global and country key Novo Nordisk staff

Attachments I and II (if applicable) to the protocol are located in the Trial Master File.

Content: Global key staff and Country key staff

It is recognised that treatments differ between different regions and countries. Likewise, specific titration guidelines may not be applicable in certain clinical situations. It is important that other information, such as symptoms of hypo/hyperglycaemia, previous response to dose adjustments, other glucose measurements and other indicators of the subject's level of glycaemic control, is taken into consideration when decisions on dosing are made. The investigator should always use his clinical judgement to avoid safety hazards. The investigator is responsible for the treatment of the subjects and can therefore overrule the guideline.

To optimise and maintain glycaemic control, the investigator should, throughout the trial, be at least in weekly contact with the subjects to assist the subjects in adjusting insulin doses and to ensure the subject's welfare.

2 Treatment regimens

At randomisation all subjects will be randomised in a 1:1 manner into two parallel treatment groups:

- Insulin degludec/insulin aspart (IDegAsp) OD ± OADs
- Insulin glargine (IGlar) OD + insulin aspart (IAsp) OD ± OADs

First dosing should take place on day of randomisation or on the day following randomisation.

There are no minimum or maximum doses for IDegAsp, IGlar or IA Sp.

2.1 Injection area

Both IDegAsp, IGlar and IA Sp should be injected subcutaneously into the thigh, upper arm (deltoid region) or the abdomen.

The injection site should remain the same throughout the trial. Rotation of injection sites within a given region is recommended.

2.2 Time of injection

IDegAsp OD will be administered with the largest meal. From week 26 subjects in need of intensification will be administered IDegAsp BID with the two largest meals; one being dinner.

During intensification the timing of IDegAsp (BID) dosing can be changed at the discretion of the investigator, but one of doses must be administered with the dinner.

IGlar will be administered OD according to local labelling.

IA Sp OD should be administered with the largest meal. From week 26 subjects in need of intensification should be administered IA Sp BID with the largest and second largest meal. From week 32 subjects in need of further intensification should be administered IA Sp TID with largest and second largest meals and the third meal of the day. Extra bolus dosing should be avoided, except for short term safety reasons. Extra bolus doses and reasons should be documented in the diary.

3 Initiation and titration

3.1 Initiation of IGlar

Subjects receiving OD basal insulin will transfer unit-to-unit to IGlar OD. Subjects receiving more than OD basal insulin should reduce the initial total daily dose by 20% or according to local labelling and transfer to IGlar OD.

3.2 Initiation of IDegAsp

Subjects receiving basal insulin OD or more will transfer unit-to-unit to IDegAsp OD.

3.3 Initiation of IAsp

IAsp will be initiated at 4U with the largest meal.

3.4 Treatment of IGlar

During the entire treatment period IGlar doses will be titrated once weekly by the investigator based upon the subject's SMPG levels and the insulin titration guideline in connection with the scheduled visits/phone contacts.

Dose adjustment will be based on the three pre-breakfast SMPG values measured on the day of the titration and the two days prior to the titration in accordance with [Table 1](#) and [Table 2](#).

Table 1 Increase of IGlar

Mean pre-breakfast SMPG		Dose adjustment
mmol/L	mg/dL	U
4.0 – 5.0	71 – 90	No adjustment
5.1 – 7.0	91 – 126	+2
7.1 – 8.0	127 – 144	+4
8.1 – 9.0	145 – 162	+6
> 9.0	> 162	+8

If one or more SMPGs values are missing, the adjustment should be performed on the remaining SMPG value(s).

Table 2 Dose reduction of IGlar

Lowest pre-breakfast SMPG		Dose adjustment
mmol/L	mg/dL	U
3.1 – 3.9	56 – 70	-2
< 3.1	< 56	-4

3.5 Treatment during week 1-26 of IDegAsp and IAsp

During the entire treatment period insulin doses will be titrated once weekly by the investigator based upon the subject's SMPG levels and the insulin titration guideline in connection with the scheduled visits/phone contacts.

3.5.1 Titration of IDegAsp OD

Dose adjustment will be based on the three pre-breakfast SMPG values measured on the day of the titration and the two days prior to the titration in accordance with [Table 3](#) and [Table 4](#).

Table 3 Increase of IDegAsp OD

Mean pre-breakfast SMPG		Dose adjustment
mmol/L	mg/dL	U
4.0 – 5.0	71 – 90	No adjustment
5.1 – 7.0	91 – 126	+2
7.1 – 8.0	127 – 144	+4
8.1 – 9.0	145 – 162	+6
> 9.0	> 162	+8

If one or more SMPGs values are missing, the adjustment should be performed on the remaining SMPG value(s).

Table 4 Dose reduction of IDegAsp OD

Lowest pre-breakfast or pre-dinner SMPG		Dose adjustment
mmol/L	mg/dL	U
3.1 – 3.9	56 – 70	-2
< 3.1	< 56	-4

3.5.2 Titration of IA_{Sp}

IA_{Sp} will be dosed once daily with the largest meal.

Dose adjustment will be based on the three pre-prandial or bedtime SMPG values measured on the three days prior to titration in accordance with [Table 5](#).

- Breakfast dose will be adjusted based on pre-lunch SMPG values
- Lunch dose will be adjusted based on pre-dinner SMPG values
- Dinner dose will be adjusted based on bedtime SMPG values

Table 5 Adjustment of IA_{Sp}

Pre-prandial or bedtime SMPG		Dose adjustment U	Rules for dose adjustments
mmol/L	mg/dL		
< 4.0	< 71	-1	≥ 1 SMPGs below target
4.0 – 6.0	71 – 108	0	0–1 SMPG above target No SMPGs below target
> 6.0	> 108	+1	≥ 2 SMPGs above target No SMPGs below target

3.6 Treatment after week 26 of IDegAsp and IA_{Sp}

If HbA_{1c} taken at week 25 is <7.0%, the subject should be titrated at week 26 according to [Table 3](#) and [Table 4](#).

If HbA_{1c} taken at week 25 is ≥ 7.0% IDegAsp treatment should be intensified to BID at week 26 as described below.

At week 32 subjects still on IDegAsp OD should be intensified to BID if HbA_{1c} taken at week 31 is ≥ 7.0%.

Intensification from IDegAsp OD to BID should be done by splitting the total daily dose of IDegAsp OD into two doses of IDegAsp. The split can be even or uneven as based on the size of the meals. Subjects with HbA_{1c} < 7.0% measured at week 25 or 31 can be switched to IDegAsp BID at weeks 26 or 32 at the discretion of the investigator based on the needs of the individual subject.

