5.3.1 Treatment regimens arms

Subjects will be randomised into a 1: 1 manner as described in Section [5.1](#) into the two stepwise treatment intensification arms below and treated as described in Section [5.3.3](#):

IDegAsp arm:

- Initial 26 weeks: IDegAsp OD administered at the largest meal each day ± OAD(s)
- Intensification period – Week 26-38: IDegAsp OD/BID administered at the largest meal(s) each day based on individual needs ± OAD(s)

IGlar + IAsp arm:

- Initial 26 weeks: IGlar OD administered in accordance with local labelling and IAsp OD administered at the largest meal ± OAD(s)
- Intensification period – Week 26-38: IGlar OD administered in accordance with local labelling and IAsp 1-3 times daily administered at main meals based on individual needs ± OAD(s)

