5.3.3 Trial insulin treatment

Subjects will receive either IDegAsp OD or IGlar OD + IAAsp OD during the first 26 weeks and continue into a 12-week intensification period.

Subjects on a pre-trial BID/TID basal insulin regimen will be shifted to OD dosing in accordance with the Titration Guideline, [Appendix A](#).

For information about initial doses, area of injection, dosing time and the weekly dose adjustments during the initial treatment period (week 2-26), refer to the Titration Guideline, [Appendix A](#).

At week 26 (V28), subjects not achieving sufficient glycaemic control ($V27 \text{ HbA}_{1c} \geq 7\%$) will be further intensified from either IDegAsp OD to IDegAsp BID or IGlar OD + IAAsp OD to IGlar OD + IAAsp BID. Subjects in good glycaemic control ($V27 \text{ HbA}_{1c} < 7\%$) will continue their insulin treatment regimen.

At week 32 (V34), glycaemic control will be evaluated again, and subjects in good glycaemic control ($V33 \text{ HbA}_{1c} < 7\%$) will continue their insulin treatment regimen. Subjects on IDegAsp OD not reaching the glycaemic target ($V33 \text{ HbA}_{1c} \geq 7\%$) will be intensified to IDegAsp BID, whereas subjects in the IGlar arm not reaching glycaemic control will be intensified with one additional IAAsp dose to IGlar OD + IAAsp BID or TID daily for the remaining six weeks of the intensification period.

Information about doses, dosing time and dose adjustments during the treatment intensification period (week 27-38) can be found in the Titration Guideline, [Appendix A](#).

Information about insulin treatment in the ‘washout’ period between the EOT visit (V40) and the 7-day follow-up visit (V41) can be found in Section [5.5](#).

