8.3.1.1 Self-measured plasma glucose used for insulin dose adjustment

Subjects should be asked to perform SMPG recordings on three consecutive days prior to the weekly dose adjustment. The number and timing of the SMPG measurements varying from 1 SMPG to 4 SMPGs per day, depending on the treatment arm, to which the subject is randomised and the subject's individual need for treatment intensification and thus the number of insulin dose administrations as specified below:

- IDegAsp OD: 1 SMPG/day
- IDegAsp BID: 2 SMPGs/day
- IGlar OD + IA Sp OD 1-2 SMPGs/day (depending on timing of IA Sp dose)
- IGlar OD + IA Sp BID 2-3 SMPGs/day (depending on timing of IA Sp doses)
- IGlar OD + IA Sp TID 3-4 SMPGs/day (depending on the timing of IA Sp doses)

These SMPG recordings are required for the individual and optimal dose adjustment and maintenance as described in the Titration Guideline, [Appendix A](#).

8.3.1.2 9-point self-measured plasma glucose profiles

9-point SMPG profiles will be used to evaluate blood sugar fluctuations and will be performed five times during the trials, refer to the flow chart (Section [2](#)).

9-point SMPG profiles should be measured starting in the morning two days prior to the scheduled visit at the time points described below – for details to be recorded in the diary see Section [8.1.5](#):

1. Before breakfast (two days prior to visit)
2. 90 minutes after start of the breakfast
3. Before lunch
4. 90 minutes after start of the lunch
5. Before dinner/main evening meal
6. 90 minutes after start of the dinner/main evening meal
7. At bedtime (two days or one day prior to visit depending on actual clock time)
8. At 4 a.m. (one day prior to visit)
9. Before breakfast at the following day (one day prior to the visit)

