3.6.2 Titration of IAsp

If HbA_{1c} at week 26 is <7.0%, the subject should continue on IAsp OD and titration according to [Table 5](#).

If HbA_{1c} at week 26 is ≥ 7.0% IAsp treatment should be intensified with a second dose of IAsp. The second dose should be initiated at 4U. Titration should be performed according to [Table 5](#).

If HbA_{1c} at week 32 is ≥ 7% IAsp treatment should be intensified with an additional dose of IAsp initiated at 4U. Titration should be performed according to [Table 5](#).

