3.7 Deviations from the algorithm

It is recommended that the algorithm is followed. However, it is also important that the decision to adjust the insulin doses is based on all relevant information as described in Section 1. A reason for deviating from the algorithm should be entered into the eCRF.

4 Data collection

The following data should be entered into the eCRF within 24 hours (on weekdays) after a site visit/phone contact:

- Per protocol SMPG values measured since last visit/telephone
- Date, time and doses of IDegAsp, IGlar and IAsp
- Prescribed doses of IDegAsp, IGlar and IAsp
- Reasons for deviation from the titration algorithms, if applicable
- Hypoglycaemic episodes

5 Review procedure

Surveillance of titration data will be performed centrally by Novo Nordisk in an unbiased manner. It is important that data regarding dose titration is entered into the eCRF within 24 hours (on weekdays). If delays occur, action cannot be taken in due time before the subject's next site visit/phone contact. The aim is to reduce the time periods in which a subject may receive suboptimal treatment.

The data listed in section [4](#) will be reviewed by Novo Nordisk within 24 hours (on weekdays). The reviewer may contact the investigator to get clarification regarding the reason for deviation or to request entry of missing data.

When the investigator receives an inquiry, a response should be received at Novo Nordisk within 24 hours (on weekdays).

During the trial HbA_{1c} will be monitored by Novo Nordisk for additional surveillance of the glycaemic control. Novo Nordisk may be in contact with sites (visit or phone contact) to discuss progress in glycaemic control and titration of individual subjects based on SMPGs and HbA_{1c}. This will be done in an unbiased and whenever possible blinded manner.

6 References

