Subjects will remain in the same treatment arm throughout the trial, with the possibility of intensification of their treatment. At week 26 (V28), subjects not achieving sufficient glycaemic control (V27 HbA_{1c} ≥ 7%) will be further intensified from either IDegAsp OD to IDegAsp BID or IGlar OD + IAsp OD to IGlar OD + IAsp BID, whereas subjects in good glycaemic control (V27 HbA_{1c} < 7%) will continue their insulin treatment regimen.

At week 32 (V34), glycaemic control will be evaluated again, and subjects in good glycaemic control (V33 HbA_{1c} < 7%) will continue their insulin treatment regimen. Subjects on IDegAsp OD not reaching the glycaemic target (V33 HbA_{1c} ≥ 7%) will be intensified to IDegAsp BID, whereas subjects in the IGlar arm not reaching glycaemic control will be intensified with one additional IAsp dose to IGlar OD + IAsp BID or TID daily for the remaining six weeks of the intensification period.

Further details

For further details on trial design and endpoints please see the NN5401-4266 protocol version 4.0.

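### Appendix A 3.6 lets IDegAsp subjects with HbA1c below 7% be intensified to BID, contrary to Protocol 5.3.3 and SAP 1.1, with no matching option in the comparator arm

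*Protocol*

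**What the plan says.** The rule for subjects at target appears in four places.

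- **Protocol 5.3.3** covers both arms at both decision points. Subjects below 7% at V27 stay on their regimen. Those below 7% at V33 "will continue their insulin treatment regimen. Subjects on IDegAsp OD not reaching the glycaemic target" are then the ones it sends to BID. It states no discretion below 7%.
- **SAP 1.1** repeats the rule: "subjects in good glycaemic control (V27 HbA_{1c} < 7%) will continue their insulin treatment regimen".
- **Appendix A 3.6** (IDegAsp arm) first says that a subject below 7% at week 25 is titrated on the once-daily tables. It ends with an exception: "Subjects with HbA_{1c} < 7.0% measured at week 25 or 31 can be switched to IDegAsp BID at weeks 26 or 32", as the investigator judges the subject's needs.
- **Appendix A 3.6.2** (comparator arm) has no such exception: "If HbA_{1c} at week 26 is <7.0%, the subject should continue on IAsp OD". At week 32 it describes an added IAsp dose only for HbA1c of 7% or more.

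Three other texts bear on the reading. Protocol 5.1 and 5.3.1 describe weeks 26-38 in terms of individual need in both arms; for the comparator, "IAsp 1-3 times daily administered at main meals based on individual needs". Appendix A section 1 says that the investigator "can therefore overrule the guideline". Appendix A 3.7 adds: "A reason for deviating from the algorithm should be entered into the eCRF".

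**The concern.** The appendix contradicts the protocol body on who may be intensified, and it does so for one arm only. Investigators know the allocation, so a discretionary step open to one arm can be used selectively.

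Comparing the two stepwise strategies at 38 weeks is a stated secondary objective. Week-38 change in HbA1c, week-38 HbA1c below 7%, and hypoglycaemia and adverse events over 38 weeks are key supportive endpoints chosen for disclosure. A reader of the SAP would take it that intensification was driven by an HbA1c of 7% or more in both arms. If some IDegAsp subjects went to BID while already at target, the strategy compared is not the one described. Protocol 6.9 also presents the OD-to-BID step as one for subjects who miss the target on OD treatment.

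**Working it through.** **1. The rules side by side for a subject below 7%**

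| Source | IDegAsp arm | IGlar + IAsp arm |
|---|---|---|
| Protocol 5.3.3, SAP 1.1 | Continue | Continue |
| Appendix A 3.6 / 3.6.2 | Continue OD, or BID at the investigator's discretion | Continue IAsp OD |
| Appendix A 3.7, if intensified anyway | Not a deviation | Deviation; reason to be entered in the eCRF |

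The first two rows disagree for IDegAsp. The last two rows differ between arms.

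**2. Is this a leftover of the amendment?** No. Global amendment 1 lists no change to Protocol 5.3.3 or Appendix A 3.6. Its change to Appendix A 3.6.2 makes the extra week-32 IAsp dose discretionary at 7% or more. It adds no option below 7%.

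**3. Which endpoints can be reached?** The switch is made at week 26 (V28) or week 32 (V34). The primary endpoint is HbA1c change to week 26, so the switch comes too late to affect it. The same holds for the 26-week hypoglycaemia endpoints and the 528-subject calculation. What remains is the week-38 and 38-week endpoints. For HbA1c below 7% at week 38, a switched subject was already below 7% at the decision, so the switch can only affect whether that status is kept.

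**4. How large could the HbA1c effect be?** The documents give neither the number switched nor the gain from switching.

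- Inputs from the sample size section: SD 1.3%, 264 per arm.
- Assumptions: the same SD and numbers hold at week 38, and each switched subject gains 0.1 to 0.3 HbA1c points.
- Half-width of the 95% confidence interval for the difference: 1.96 × 1.3 × √(2/264) = 0.222.
- Shift in the arm mean = share of arm switched × gain per switched subject.
- Share needed for a shift of one half-width: 0.222/0.3 = 0.74, or 74% of the arm; at the lower gain, 0.222/0.1 = 2.22, which is over 200% of the arm and impossible.
- For each tenth of the arm switched, the shift is 0.1 × 0.1 = 0.01 to 0.1 × 0.3 = 0.03 points.

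Only subjects below 7% can be switched under this sentence, which limits the share further. No comparable figure can be derived for hypoglycaemia, because the documents give no rates.

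**The case against.** The best defence is that the documents allow for judgement anyway. Protocol 5.3.3 refers to Appendix A for doses and adjustments in weeks 27-38. Sections 5.1 and 5.3.1 speak of individual need, and the investigator may overrule the guideline in either arm. On this view the comparator faces only an extra documentation step, not a prohibition. Nor are the two steps alike: the IDegAsp switch splits the existing daily dose, whereas the comparator step adds a new 4 U injection. SAP 1.1 is a design summary, and no planned analysis conditions on regimen.

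Much of this stands, and it is why the point is minor. It does not remove the conflict. The individual-need wording is general and covers both arms, so it does not explain an explicit exception for one. The overrule clause still leaves the step inside the algorithm for IDegAsp and outside it for the comparator. The 5.3.3 rule for subjects below 7% is specific and carries no exception.

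A reader comparing Appendix A with the protocol body might also infer that Protocol 8.3.1.1 understates the comparator's daily glucose measurements, for example "IGlar OD + IA Sp OD 1-2 SMPGs/day (depending on timing of IA Sp dose", on the ground that pre-breakfast plus one value per IAsp dose always makes 2, 3 or 4. The documents do not support this, because the day windows differ. IGlar uses the titration day and the two days before (Appendix A 3.4); IAsp uses the three days before (3.5.2). Three days before titration only IAsp values are needed: 1, 2 or 3 for IAsp OD, BID or TID. On the next two days both are needed: 2, 3 or 4. Over the three days before titration the counts are therefore 1-2, 2-3 and 3-4, as stated. A flat 2, 3 and 4 would itself be wrong three days before titration and on the titration day. Only the remark that the range depends on IAsp timing explains it poorly, which is editorial.

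**Conclusion.** The conflict is real and minor. One sentence in Appendix A 3.6 contradicts Protocol 5.3.3 and SAP 1.1, and it makes intensification below 7% part of the algorithm in the IDegAsp arm only. It bears on the supportive week-38 comparisons and on nothing earlier.

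Three stronger inferences are not supported.

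- **That the primary non-inferiority result is at risk.** The switch comes at V28 or later.
- **That the rule favours IDegAsp.** It splits an existing dose in subjects already at target, and nothing in the documents fixes the direction for HbA1c or hypoglycaemia.
- **That comparator subjects were barred from intensification below 7%.** The investigator could overrule the guideline, giving a reason.

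That the effect is probably small rests on the assumed gain of 0.1 to 0.3 points and on carrying the planned SD and numbers to week 38. The textual conflict needs no assumption.

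**What to change.** Before or during conduct, either delete the discretionary sentence in Appendix A 3.6, or give both arms the same discretion below 7% and write it into Protocol 5.3.3, Appendix A 3.6.2 and SAP 1.1. The cost is a wording change.

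If conduct is past, report by arm the number of subjects intensified at week 26 or 32 with V27 or V33 HbA1c below 7%, next to the week-38 results. Derive the count from recorded doses and HbA1c. The eCRF deviation reasons would not do, since an IDegAsp switch below 7% needs none. Doses go into the eCRF under Appendix A section 4 and HbA1c comes from the central laboratory, so this is one table from data already collected.
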